# **Objectives**

Can an intubation barrier box be used during induction without any significant delay in time to intubate (TTI)?

**Research question**: Comparing time to intubate (TTI) with/without intubation barrier box in study group vs control group when used with video laryngoscopy (glidescope) during for anesthetic induction.

## **Setting of the Human Research**

This study will take place in the operating room at the Robert Packer Hospital by the Anesthesiology Department and will involve only procedures that are part of routine care.

## **Background**

The COVID-19 outbreak has presented unprecedented challenges and risks to health care personnel and pose unique challenges to airway management secondary to aerosol generation. The absolute risk increase is between 10% (cohort studies) and 15% (case-control studies) for transmission of SARS-CoV-1–associated infection to health care personnel performing intubation. Recent changes to airway management of confirmed positive COVID-19 or persons under investigation (PUI) involve the use of full personal protective equipment (PPE) including N95 masks and the routine use of video laryngoscopy when accessible. Unrecognized asymptomatic and presymptomatic infections with SARS- CoV-2 virus might contribute to transmission. Clinicians have been compelled to improvise protective barrier enclosures for use during endotracheal intubation to minimize aerosol exposure to operating room personnel. We decided to evaluate time to intubate with an intubation barrier box to demonstrate safe use for routine anesthetic inductions during this pandemic era.

# **Funding:**

NONE

# **Study Design:**

Prospective randomized controlled trial

#### **Recruitment methods:**

Source of participants: Patients undergoing elective surgery at Robert Packer hospital

Patient will be recruited in pre-operative clinic after surgery date has been finalized.

Patients will be invited to take part and provided a letter of invitation. The researcher will answer any questions and verbal consent will be obtained.

# **Total participants:**

The study plans to enroll approximately 72 subjects to two groups with 36 subjects in each group. This sample size is based on the estimated time difference of 10 seconds between intubation times with and without the box.

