## Statistical analysis plan:

#### Sample size calculation

Sample size calculation was done by using the two means equation in the Power and Sample Size Calculation program (Dupont and Plummer, 1990). Based on a study by Teoh et. al., (2019), the mean of intubation time for Glidescope was 31.2 seconds and Airway Scope was 20.6 seconds. A clinically significant effect of 10 seconds would be of interest. The two-tailed hypothesis testing concluded that each group needed 36 subjects to achieve a power of 80%, with an error rate of 5%. A total of 90 subjects will be enrolled in this study with an estimated dropout rate set at 20%, 45 subjects will be enrolled in each group.

Suggested citation for Power and Sample Size Software:

Dupont WD, Plummer WD: 'Power and Sample Size Calculations: A Review and Computer Program', Controlled Clinical Trials 1990; 11:116-28.

Reference article:

It is a standard practice to include a dropout rate of 20% for clinical trials so that the power of the study will not be affected by dropouts, missing data and other study deviations (https://online.stat.psu.edu/stat509/node/47/).

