Statistical Analysis Plan

Date November 20, 2024

Title: Time to Adapt in the Pandemic Era: A Prospective Randomized Study Comparing Time to Intubate With and Without the Barrier Box

Principal Investigator: [name]

Sub-Investigators: [name], [name], [name]

Research Site: Guthrie Robert Packer Hospital, Department of Anesthesiology

National Clinical Trial Number: NCT04411056

Sample size calculation

Sample size calculation was done by using the two means equation in the Power and Sample Size Calculation program (Dupont and Plummer, 1990). Based on a study by Teoh et. al., (2019), the mean of intubation time for Glidescope was 31.2 seconds and Airway Scope was 20.6 seconds. A clinically significant effect of 10 seconds would be of interest. The two-tailed hypothesis testing concluded that each group needed 36 subjects to achieve a power of 80%, with an error rate of 5%. A total of 90 subjects will be enrolled in this study with an estimated dropout rate set at 20%, 45 subjects will be enrolled in each group.

Suggested citation for Power and Sample Size:

Dupont WD, Plummer WD: 'Power and Sample Size Calculations: A Review and Computer Program', Controlled Clinical Trials 1990; 11:116-28.

Reference article;

It is a standard practice to include a dropout rate of 20% for clinical trials so that the power of the study will not be affected by dropouts, missing data and other study deviations (https://online.stat.psu.edu/stat509/node/47/).

May 5, 2020 Statistical Consultant KV

The study plans to enroll approximately 72 subjects to two groups with 36 subjects in each group. This sample size is based on the estimated time difference of 10 seconds between intubation times with and without the box. (Protocol April 30, 2020)

Randomization:

Subjects will be randomized by block randomization. Randomization will be done by a random number generated computer program by someone not involved in the research. The randomization schedule will be placed in sealed envelopes to be concealed from the researcher until time of verbal consent.

Sealed Envelope Ltd. 2019. Simple randomisation service. [Online] Available from: https://www.sealedenvelope.com/simple-randomiser/v1/ [Accessed 6 May 2020].

Statistical Software

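### The protocol's Total participants section gives the evaluable number (72) as the number to enrol, while the sample size calculation enrols 90

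*Protocol*

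**What the plan says.** The documents give two enrolment figures.

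- **Protocol, Total participants:** "The study plans to enroll approximately 72 subjects to two groups with 36 subjects in each group". The section ties this number to a 10 s difference between intubation with and without the box. It does not mention dropout.
- **Protocol, Sample size calculation (under Statistical analysis plan):** "The two-tailed hypothesis testing concluded that each group needed 36 subjects to achieve a power of 80%, with an error rate of 5" per cent. The effect is stated as "A clinically significant effect of 10 seconds would be of interest". The section then allows for 20% dropout and says "A total of 90 subjects will be enrolled in this study" and "45 subjects will be enrolled in each group". The stated reason for the allowance is to protect power against losses, gaps in the data and departures from plan.
- **SAP, Sample size calculation:** repeats the calculation that ends at 90, followed by the date May 5, 2020. It then repeats the sentence about 72, with the tag "Protocol April 30, 2020".

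Neither document says that 72 is the evaluable number and 90 the enrolled number, or which of the two applies.

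**The concern.** Both sentences are about enrolment, so they cannot both be the target. The gap is 18 subjects, which is 25% of 72 and more than the word approximately can cover.

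The enrolment target decides when recruitment stops, and a later reader uses it to judge whether the trial met its plan. A team working from Total participants would stop at 72 and give up the whole dropout allowance. The protocol provides for losses after enrolment. Under Routine procedures for all patients, subjects are withdrawn after more than three attempts by an experienced provider, and are excluded for equipment malfunction or for delays unrelated to care.

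**Working it through.** **Inputs from the documents.** 36 per group needed; 80% power; 5% two-tailed error; 10 s difference; 20% dropout; equal groups. No SD is given. The only source figures are two means: "the mean of intubation time for Glidescope was 31.2 seconds and Airway Scope was 20.6 seconds".

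**1. Reproduce the plan's enrolment figure.**
36/(1 − 0.20) = 45 per group, and 2 × 45 = 90. This matches exactly. After 20% loss, 45 × 0.80 = 36 per group, or 72 in all. So 36 per group is the number required after losses.

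**2. Apply the same loss to 72 enrolled.**
72 × 0.80 = 57.6, or 28.8 per group (28 to 29).

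**3. Back-solve the SD, as an assumption.**
The 36 per group cannot be checked forward without an SD. In the normal approximation, power = Φ(d/(SD·√(2/n)) − 1.960). Power of 80% at n = 36 requires d/(SD·√(2/36)) = 1.960 + 0.842 = 2.802. For d = 10 s:

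SD = 10 × √18/2.802 = 15.1 s (14.9 s with the noncentral t).

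For the 10.6 s difference between the two source means (31.2 − 20.6), it is about 16 s.

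**4. Power at the reduced size.**
The quantity 2.802 scales with √(n/36), so SD and d cancel.

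| Analysed per group | Calculation | Power, normal | Power, noncentral t |
|---|---|---|---|
| 36 | Φ(2.802 − 1.960) | 80.0% | 80.0% |
| 29 | Φ(2.802 × √(29/36) − 1.960) = Φ(0.555) | 71.0% | 70.7% |
| 28 | Φ(2.802 × √(28/36) − 1.960) = Φ(0.511) | 69.5% | 69.2% |

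The loss is about 9 to 11 percentage points. It is the same for any SD and difference that give 80% at 36 per group.

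**5. What this does not measure.**
The SAP's primary analysis is a one-sided t-test of non-inferiority with a 15 s margin, and its power is stated nowhere. With an assumed SD of about 15 s and one-sided 5%, it would be:

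| True difference | 29 per group | 36 per group |
|---|---|---|
| 0 s | about 98% | about 99% |
| 5 s | about 80% | about 87% |
| 10 s | about 34 to 35% | about 40% |

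Power for that test depends far more on the true difference than on whether 29 or 36 per group are analysed.

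**The case against.** **The SAP shows where each figure comes from.** It attributes the 72 to the protocol of April 30, 2020 and dates the calculation behind the 90 five days later. A reader might infer two rival enrolment plans, but the dates point to an older figure that was not updated. This stands, and it makes 90 the likelier intended target. It does not remove the conflict. Total participants carries no such label and is current protocol text, and the SAP repeats both figures without choosing.

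**The power loss belongs to a test that is not the primary analysis.** A reader might infer that stopping at 72 would leave the non-inferiority comparison underpowered. The documents do not support that. The 80% is for a two-sided test of a 10 s difference. Under the assumed SD of about 15 s, the non-inferiority test at 29 per group has high power if the box adds nothing. If the box truly adds 10 s, power is low even at 36 per group, so enrolling 90 would not repair it. This stands and limits the claim to the stated calculation.

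**The 20% is a convention.** The plan justifies it as usual practice, and participation is limited to time in the operating room. Actual loss could be smaller. This also stands, but 20% is the plan's own assumption, and some loss is plausible under its withdrawal and exclusion rules.

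**No arithmetic is wrong.** Correct: 36, 45, 72 and 90 agree with one another. The fault is that an evaluable number is labelled as an enrolment number.

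**Conclusion.** The point holds as an inconsistency in a number the trial acts on. Total participants states the evaluable number as the enrolment target, against the 90 in the sample size calculation of both documents. Under the plan's 20% dropout, stopping at 72 would leave about 29 per group, and power for the stated two-sided 10 s calculation would be about 71% (69 to 71% for 28 to 29 per group) instead of 80%. This rests on taking the stated 80% at 36 per group as given, which cannot be verified without an SD. The size of the fall does not depend on the SD. It says nothing about the adequacy of the planned non-inferiority test.

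**What to change.** - **Protocol, Total participants:** write *90 subjects enrolled (45 per group) to give 72 evaluable (36 per group)*.
- **SAP, Sample size calculation:** delete the sentence about 72 or mark it as superseded. It should not be changed to 90 while still attributed to the April 30, 2020 protocol, because that would misreport its source.
- **If 72 was the real enrolment target:** remove the 90 and the dropout allowance from both documents, and state that power for the two-sided 10 s calculation is about 71% after 20% dropout. Label it as belonging to that calculation, not to the non-inferiority test.

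The cost is a few words, and 90 is already the plan's own figure. The documents do not give the recruitment status. If enrolment had ended by the SAP date of November 20, 2024, the change would clarify the record but could not alter the number enrolled.

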## Inclusion criteria;

Males and females above 18 years of age who are undergoing elective surgery at Robert Packer Hospital who are tested COVID negative.

## **Exclusion criteria:**

Children, pregnant women, and prisoners, ASA 4 ,ASA5, patients with severe cardiopulmonary compromise, BMI >35, known or anticipated difficult airway, patients with positive COVID status or person under investigation.

## **Statistics:**

Comparing time to intubate (TTI) between study and control group using a t-test to compare means.

## **Study end points:**

Primary end point:

Calculating time to intubate (TTI) which is defined as time duration from loss of twitch to confirmation of end tidal CO 2.

Secondary end point:

- 1)Time duration from induction with propofol to confirmation of endotracheal tube
- 2) Need for bag mask ventilation and duration of ventilation
- 3)Episode of hypoxia as evidenced of Spo2 < 90 %
- 4) Subjective assessment of intubation by provider: easy /moderate /difficult

**Study Timelines:** 

Individual subjects participation is limited to time spent in operating room

Duration for enrolling all participants: 2 months

Estimated date to complete study: 4 months

**Procedures involved in Human research:** 

After obtaining a verbal informed consent, patients will be randomized into study

group - IB (intubation barrier box used) and control group -C (no intubation barrier

box used).

Subjects will be randomized by block randomization. Randomization will be done

by a random number generated computer program by someone not involved in the

research. The randomization schedule will be placed in sealed envelopes to be

concealed from the researcher until time of verbal consent.

After placement of intravenous line in pre- operative area, anxiolytics may be given

as per the discretion of anesthesiologist caring for the patient. After arrival to OR,

patient will be placed on standard ASA monitors. An intubation barrier box designed

by our bio -medical team will be placed at the head end of operating table in the

study group (IB) and patient will be comfortably positioned with their head on a

pillow inside the intubation box.

Patients in control group - No intubation box.

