### Routine procedures for all patients:

Patients head will be positioned in optimal position. Head- end of the operating table elevated to 20 degrees to improve pulmonary reserve. A twitch monitor is placed pre induction.

Pre oxygenation will be achieved by providing supplemental oxygen through mask with either 3 minutes of tidal volume breaths/ 8 vital capacity breaths.

Standard induction technique for both groups. All patients will be induced with standard induction doses of lidocaine 1- 1.5 mg/kg, fentanyl 1-2 mcg/kg and propofol 1-2 mg/kg followed with saline flush. After loss of consciousness is confirmed, patients will be given Succinyl choline 1.5 mg/kg total body weight (TBW) for paralysis. Apneic oxygenation will be continued after induction. Ventilation will not be performed during this time unless desaturation with spo2 less than 90 % is observed .Loss of Train of four (TOF)will be checked to confirm paralysis, and the provider will proceed with intubation.

A video laryngoscope (glidescope) with style will be used for intubation of all patients. Time to intubate (TTI) will be calculated by an independent provider not directly involved in research study. If intubation is unsuccessful by primary provider , further attempts by any other provider will be documented separately. If difficulty

to intubate is deemed secondary to intubation box, it will be removed immediately.

Intubation procedure will be performed by provider with more than 3 years of

experience and has performed at-least 3 intubations with intubation barrier box with

patients.

Timing of all events will be performed by independent provider.

Other data points calculated.

Induction time – loss of spontaneous ventilation to placement of ETT.

Episode of hypoxia defined by spo2 < 90 %

Time duration of bag –mask ventilation if needed.

Source record: Electronic medical record

Long-term data collection: None

Withdrawal of participants:

Unanticipated difficult intubation as described by > 3 attempts by experienced

provider.

Patients in the study will be excluded secondary to any equipment malfunction

or unforeseen delays not related to patient care.

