#### **Consent process:**

Due to the prospective design of the study, a consent will be taken. Consent will be obtained verbal rather than written. A waiver of consent documentation is requested from the IRB because the research presents no more than minimal risk of harm to subjects, and the research involves no procedures for which written consent is normally required outside of the research context and is part of routine anesthesia patient care. The verbal consent will take place during pre- operative assessment prior to the surgery by a member of research team .

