#### **Randomization:**

Sealed Envelope Ltd. 2019. Simple randomisation service. [Online] Available from: https://www.sealedenvelope.com/simple-randomiser/v1/ [Accessed 6 May 2020]. Randomization will remain concealed from the researchers until the time of the verbal informed consent.

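### The plan lets the arm be known from verbal consent onward, and nothing requires eligibility to be confirmed or the intubating provider named before disclosure

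*Protocol*

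**What the plan says.** The concealment rule appears three times. The Protocol, under Procedures involved in Human research, has the schedule in sealed envelopes, "concealed from the researcher until time of verbal consent". The Protocol's Randomization section says "Randomization will remain concealed from the researchers until the time of the verbal informed consent". The SAP's Randomization section repeats the sentence from Procedures involved in Human research.

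On timing, the Protocol's Recruitment methods state "Patient will be recruited in pre-operative clinic after surgery date has been finalized", and its Consent process section states "The verbal consent will take place during pre- operative assessment prior to the surgery by a member of research team". The order of consent and allocation is explicit: "After obtaining a verbal informed consent, patients will be randomized into study" or control group. Induction, intubation and every planned endpoint follow in the operating room, and Study Timelines limits a subject's participation to the time spent there.

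Three other provisions bear on the interval between consent and induction:

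- **Eligibility.** Patients must be people "who are tested COVID negative". The date of the test relative to consent is not given.
- **Provider.** "Intubation procedure will be performed by provider with more than 3 years of" experience, who has also done at least 3 box intubations on patients. Nothing says who assigns the provider, when, or whether the arm is known at that point.
- **Exclusion after entry.** Patients may be excluded for equipment malfunction "or unforeseen delays not related to patient care". No decision-maker is named.

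**The concern.** The box is visible, so the intubating provider cannot be blinded, and the documents describe no blinding. In such a trial, protection against selection before induction depends largely on how long the arm stays unknown. The stated rule lifts concealment at consent and puts nothing in its place.

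Two routes to bias are then open. First, whoever assigns the provider may already know the arm, and neither randomization nor analysis is stratified by provider. Second, losses between disclosure and induction may depend on the arm. The Protocol's Risk to participants section itself names a mechanism: the box may cause claustrophobia. A patient who learns in advance of a box allocation has a reason to decline that a control patient does not have.

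Direction matters because the primary question is non-inferiority. If slower patients are lost from the box arm, or faster providers are assigned to it, the estimated difference moves toward a finding of non-inferiority.

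**Working it through.** **1. The sequence in the documents.** Recruitment and verbal consent (pre-operative clinic or assessment) → randomization, with the arm no longer required to be concealed → unstated interval → operating room, induction, intubation, endpoints. No text closes the interval by tying the opening of the envelope to confirmed eligibility or a named provider.

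**2. The plan's own figures.** The sample size sections give 36 per arm and 20% dropout: 36 / (1 − 0.20) = 45 per arm, 90 in total, as stated. The plan thus allows for 45 − 36 = 9 losses per arm. It does not say how many would fall before induction.

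No SD is stated. For a 10 s difference, two-sided 5% and 80% power, the normal formula with SD 15 s gives n = 2 × (1.960 + 0.842)² × 15² / 10² = 35.3, rounded up to 36. The SD implied by exactly 36 is 15.1 s (14.9 s by the t-based formula). An SD of 15 s is assumed below.

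**3. A simple example (all inputs assumed).** Of 45 box patients, 3 would have a TTI of 70 s and 42 a TTI of 40 s. Full mean: (3 × 70 + 42 × 40) / 45 = 42.0 s. If the 3 are lost before induction, the mean is 40.0 s. The shift is 2.0 s, and 2.0 / 15 = 13% of the margin.

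**4. A range (assumed).** Let 20% of the box arm be lost, with correlation ρ between loss and TTI, and let control losses be unrelated to TTI. The shift in the box mean is ρ × SD × φ(0.842) / 0.80, where φ(0.842) = 0.280. With SD 15 s:

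- ρ = 0.25: 1.3 s
- ρ = 0.5: 2.6 s
- ρ = 1 (exactly the slowest fifth lost): 5.25 s

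At ρ = 1 the shift is 3.5 s for SD 10 s and 7.0 s for SD 20 s. Equal selective loss in both arms would cancel.

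**5. Provider imbalance (assumed).** A 20-point difference between arms in the share of faster providers, with a provider effect of 5 to 15 s, gives 0.20 × 5 = 1 s to 0.20 × 15 = 3 s.

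**6. Effect on the test.** The SAP uses a one-sided t-test at p < 0.05 with a 15 s margin. With 36 analysed per arm and SD 15 s, the standard error of the difference is 15 × √(2/36) = 3.54 s. At a true difference of 15 s, the 5% error rate rises to about 14% for a 2 s bias, 18% for 2.6 s and 43% for 5.25 s.

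**The case against.** A reader might infer that eligibility and provider are in fact unsettled when the arm is disclosed. The documents do not say so. The COVID criterion is worded as a result already in hand, and ASA class, BMI and airway assessment could all be known at the clinic. The timing of provider assignment is simply not given. Nor do the documents say that the envelope is opened in the clinic: concealment until consent sets the earliest point, not the actual one.

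A reader might also infer that the envelope could be open while consent is being sought. That fails, because the Protocol places randomization after consent, and the schedule is generated by someone outside the research and kept in sealed envelopes. Entry to the trial is concealed. Nor does any text provide for replacing lost patients.

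Existing provisions limit the risk. Every provider must meet an experience minimum, including prior use of the box. Known or anticipated difficult airways are excluded from both arms, so slow intubations are hard to foresee. A CONSORT diagram will track participants.

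These points narrow the concern but do not remove it. An experience floor does not prevent arm-aware choice among qualified providers. A flow diagram can show unequal losses but cannot correct them. The rule as written still permits early disclosure with no safeguard.

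**Conclusion.** The concern holds as a weakness in a stated rule, not as evidence that bias will occur. The plan permits the arm to be known for an unstated interval before induction and does not require eligibility to be confirmed or the provider named beforehand. It should be changed, because the remedy is specific and nearly free.

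The size cannot be estimated from the documents, which give neither loss rates, an SD nor provider effects. The 2 s example and the range of about 1 to 5 s rest wholly on assumed inputs, with SD 15 s and selective loss or faster providers favouring the box arm. The upper end is a bound that needs staff or patients to anticipate TTI perfectly. These figures show that a modest imbalance could matter against a 15 s margin and a standard error near 3.5 s; they do not forecast one.

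**What to change.** In the Protocol (Procedures involved in Human research; Randomization) and the SAP (Randomization), replace the clause that ends concealment at verbal consent with a rule such as: the envelope is opened on the day of surgery, as late as feasible before the patient is positioned, and only after final eligibility (including the COVID result and the airway assessment) has been recorded and the intubating provider named.

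The new timing must be reconciled with the anxiolytic text. Procedures involved in Human research mentions anxiolytics in the pre-operative area, before arrival in the operating room, and Risk to participants relies on them for box-related claustrophobia.

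This change limits steering and loss before induction only. Exclusions that arise in the operating room (equipment malfunction, delays, more than 3 attempts) can still be made with the arm known. They are a separate matter for the definition of the analysis set, which neither document gives.

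The cost is one sentence amended in three places, the reconciliation above, and a box on hand for every enrolled patient until the envelope is opened. The sample size is unaffected.
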